- 217 Men of reproductive potential and women of childbearing potential who are unwilling to practice a highly effective method(s) of birth control while on study through 4 months after receiving the last dose of study drug. Highly effective methods of birth control are defined as those which result in a low failure rate (ie, less than 1% per year) when used consistently and correctly such as implants, injectables, combined oral contraceptives, intrauterine devices (IUDs), sexual abstinence or vasectomised partner.
- Note: Men and women who do not meet the definitions below are considered to be of reproductive potential or childbearing potential respectively.
- Men of non-reproductive potential are defined as having azoospermia, whether due to having had a vasectomy or due to an underlying medical condition.
 - Women not of childbearing potential are defined as: Any female who is postmenopausal defined as at least 12 months with no menses without an alternative medical cause; in women < 45 years of age, a high follicle stimulation hormone [FSH] level in the postmenopausal range may be used to confirm a postmenopausal state in women not using hormonal contraception or hormonal replacement therapy; in the absence of 12 months of amenorrhea, a single FSH measurement is sufficient OR have had a hysterectomy and/or bilateral oophorectomy, or bilateral salpingectomy at least 6 weeks prior to screening, OR has a congenital or acquired condition that prevents childbearing.
- 218 Women who are lactating /breastfeeding or who plan to breastfeed while on study through 4 months after receiving the last dose of study drug.
- 219 Women with a positive pregnancy test.
- 220 Women planning to become pregnant while on study through 4 months after receiving the last dose of study drug.
- 221 Subject has known sensitivity to any of the products or components to be administered during dosing.

- 222 Subject likely to not be available to complete all protocol-required study visits or procedures, and/or to comply with all required study procedures to the best of the subject and investigator's knowledge.
- 223 History or evidence of psychiatric, substance abuse, or any other clinically significant disorder, condition or disease (with the exception of those outlined above) that, in the opinion of the investigator or sponsor physician, if consulted, would pose a risk to subject safety or interfere with the study evaluation, procedures or completion.

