6.2.4.10.2 Contraception Requirements for AMG 820 and/or Pembrolizumab

AMG 820 and/or Pembrolizumab may have adverse effects on a fetus *in utero*.

Furthermore, it is not known if AMG 820 or pembrolizumab has transient adverse effects on the composition of sperm. Non-pregnant, non-breast-feeding women may be enrolled if they are willing to use acceptable method(s) of effective contraception or are considered of non-childbearing potential. Refer to [Section 4.2](#), exclusion criteria 214, for contraception requirements and definition of women of non-childbearing potential for this study. Refer to the informed consent form for acceptable method(s) of effective contraception for subjects to use in this study. Additional country-specific contraception requirements may be defined in a country-specific protocol supplement at the end of the Appendix Section of protocol as required by local laws and regulations.

Subjects should be informed that taking AMG 820 and/or pembrolizumab may involve unknown risks to the fetus (unborn baby) if pregnancy were to occur during the treatment and for 4 months after end of pembrolizumab. In order to participate in the study they must adhere to the contraception requirements described above for the duration of the study treatment and during the follow-up period defined in [Section 9.3](#) (Pregnancy and Lactation Reporting). If there are any concerns that a subject will not reliably comply with the requirements for contraception, that subject should not be enrolled into the study.

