RADIOLOGICAL ASSESSMENTS																																			
Radiographic (CT or MRI.) Scans & Tumor Assessment ^{(a)(i)}	X																																X	X	X ^c
Dosing																																			
AMG 820 ^(g)			X								X										X												X	X	
Pembrolizumab ^(g)			X								X										X												X	X	
PK ASSESSMENTS																																			
AMG 820 PK collection ^(k)		X		X	X	X	X	X	X	X	X	X	X	X	X	X	X	X	X	X	X	X	X	X	X	X	X	X	X	X	X	X	X	X	

EOI = End of Infusion; LTFU = Long Term Follow-Up; Q3W = Every 3 Weeks; Q6W = Every 6 Weeks; Q4C = Every 4 Cycles

^a Procedures to be performed ≤ 28 days prior to enrollment

^b Safety follow-up will be performed 135 (+7) days after the last dose of AMG 820 or the last dose of pembrolizumab, whichever is later. Suggested frequency of visits to follow any continuing events are approximately: every week for SAEs, Q2W for grade 3 or higher AEs (excluding AST elevation without drug-associated hepatotoxicity), and Q3W for other abnormalities until resolved to grade 1 or baseline.

^c Physical exam including ECOG.

^d ECG performed at screening and safety follow-up visits and as clinically indicated during the study.

^e Subjects will be followed for survival every 12 weeks (±28 days) from the date of the safety follow-up visit until up to approximately 12 months after date of enrollment. Subsequent cancer treatments and disease status will be collected as part of the long-term follow-up survival assessment.

^f Female subject of childbearing potential to have serum pregnancy test at screening; urine pregnancy test at all other time points. If urine pregnancy test is positive or cannot be confirmed as negative, a serum pregnancy test will be required.

^g AMG 820 in combination with pembrolizumab will be administered every 3 weeks.

^h Anti-AMG 820 and anti-pembrolizumab antibodies samples will be collected pre-dose and at indicated time points throughout the study.

ⁱ Tumor biopsy tissue is required per [section 7.6](#).

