7.2.2 Treatment

Treatment begins when the first dose of protocol-required therapies is administered to a subject.

The following procedures will be completed during the treatment period at the times designated in the Schedule of Assessments ([Table 5](#)). Administration of

protocol-required therapies is to be performed after all other procedures are completed during each visit that it is required, unless otherwise stated.

- Physical examination as per standard of care including ECOG performance status assessment. Physical examination findings should be recorded on the appropriate CRF (eg, medical history, adverse event)
- Vital signs (systolic/diastolic blood pressure, heart rate, respiratory rate, temperature): Subject should be in a supine position in a rested and calm state for at least 5 minutes before blood pressure assessments are conducted. If the subject is unable to be in the supine position, the subject should be in most recumbent position possible. The blood pressure position selected and temperature location for a subject should be the same that is used throughout the study and be documented on the vital signs CRF.
- Local laboratory assessments: On treatment tests can be performed within 2 days of the planned visit. Results should be reviewed prior to the administration of study treatment:
 - hematology panel
 - chemistry panel
 - lipase and amylase
 - coagulation: PT or INR and PTT or a PTT
 - thyroid function tests: T3 (or FT3), FT4, TSH
 - urinalysis
 - Serum or urine pregnancy test for female subjects of childbearing potential: Additional, on-treatment pregnancy testing may be performed at the investigator's discretion.
- Central laboratory assessments (refer to Schedule of Assessments as not all tests will be required after Amendment 2):
 - whole blood for biomarker analyses (Immunophenotyping)
 - serum for biomarker analyses of baseline circulating markers (IL34, IL10, VEGF MCP-1, MMPs, CSF-1)
 - Blood for immunogenicity (anti-AMG 820 antibody and anti-pembrolizumab antibody). Note: All samples should be drawn within 24 hours before infusion of AMG 820 or pembrolizumab and at the same time as the pre-dose trough blood collection for the PK sample.
 - blood for PK of AMG 820 and pembrolizumab
 - biomarker development blood sample
 - tumor tissue biopsy for biomarker analyses is strongly encouraged in all subjects

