7.2.3 Safety Follow-up Visit(s)

All subjects will complete a safety follow-up visit approximately 135 (+7) days after the last dose of study treatment.

The following procedures will be performed:

- Physical examination as per standard of care including ECOG performance status assessment. Physical examination findings should be recorded on the appropriate CRF (eg, medical history, event)
- Body weight in kilograms should be measured without shoes.
- Vital signs (systolic/diastolic blood pressure, heart rate, respiratory rate, temperature): Subject should be in a supine position in a rested and calm state for at least 5 minutes before blood pressure assessments are conducted. If the subject is unable to be in the supine position, the subject should be in most recumbent position as possible. The position selected and temperature location for a subject should be the same that is used throughout the study and documented on the vital sign CRF. Record all measurements on the vital signs CRF
- A 12-lead ECG per standard of care: The ECG must include the following measurements: heart rate, PR, QRS, QT and QTc intervals. Subject must be in supine position in a rested and calm state for at least 5 minutes before ECG assessment is conducted. If the subject is unable to be in the supine position, the subject should be in most recumbent position as possible. The investigator or designated site physician will review all ECGs. Once signed, the original ECG tracing will be retained with the subject's source documents. At the request of the sponsor, a copy of the original ECG will be made available to the Sponsor.
- Local laboratory Assessments
 - hematology panel
 - chemistry panel
 - lipase and amylase
 - coagulation: PT or INR and PTT or a PTT
 - thyroid function tests: T3 (or FT3), FT4, TSH
 - urinalysis
 - serum or urine pregnancy test for female subjects of childbearing potential

- Central laboratory assessments (refer to Schedule of Assessments as not all tests will be required after Amendment 2):
 - All subjects
 - Blood for immunogenicity
- Radiographic tumor imaging and tumor response assessments are to be performed if the subject ended study treatment prior to confirmed PD per irRECIST and has not had assessments performed within 6 weeks of the visit.

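### Criterion 217 lets one FSH result replace the 12 months without menses that define postmenopausal, which removes the contraception rule and all scheduled pregnancy tests for that woman

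*Protocol*

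**What the plan says.** Criterion 217 in Protocol 4.2 excludes men of reproductive potential and women of childbearing potential who will not use highly effective contraception on study and for 4 months after the last dose. Its Note sets the default: "Men and women who do not meet the definitions below are considered to be of reproductive potential or childbearing potential respectively".

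The definition of women not of childbearing potential then runs as follows:

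- The main limb is menopause: "postmenopausal defined as at least 12 months with no menses without an alternative medical cause".
- FSH is brought in for women under 45 who are not using hormonal contraception or replacement: "a high follicle stimulation hormone [FSH] level in the postmenopausal range may be used to confirm a postmenopausal state".
- The next clause reads: "in the absence of 12 months of amenorrhea, a single FSH measurement is sufficient".
- The remaining limbs are hysterectomy, bilateral oophorectomy or bilateral salpingectomy at least 6 weeks before screening, or a congenital or acquired condition that prevents childbearing.

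The classification is used elsewhere. Section 6.2.4.10.2 says: "Non-pregnant, non-breast-feeding women may be enrolled if they are willing to use acceptable method(s) of effective contraception or are considered of non-childbearing potential". Table 5, footnote f, says: "Female subject of childbearing potential to have serum pregnancy test at screening; urine pregnancy test at all other time points". Sections 7.2.1, 7.2.2 and 7.2.3 attach the same limit to testing at screening, on treatment and at safety follow-up.

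**The concern.** The clauses give FSH two incompatible roles. In the first, a postmenopausal-range value supports a state already defined by 12 months without menses. In the second, one measurement takes the place of those 12 months. The second role removes the requirement on which the definition rests.

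The classification decides who must use contraception and who is tested for pregnancy. Section 6.2.4.10.2 says that AMG 820 and pembrolizumab may harm a fetus. A woman wrongly classed as not of childbearing potential loses the two measures meant to prevent or detect an exposed pregnancy.

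**Working it through.** No arithmetic beyond a count applies. The check reads the clause each way it can be read, then follows the resulting classification through the protocol.

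**Step 1. Possible readings of the last FSH clause**

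| Reading | Who is released from the 12 months |
|---|---|
| Literal: no threshold, age limit or hormone condition is stated in the clause | Any woman with one FSH measurement |
| Postmenopausal range and no-hormone conditions carry over | A woman of any age not on hormones, with one result in range |
| The under-45 condition carries over as well | Only women under 45 not on hormones, with one result in range |

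On every reading, one result stands in for 12 months. The narrowest reading inverts the ages: women under 45 get the looser test, while women of 45 or older must complete the 12 months. The clause also does not repeat the condition that no other medical cause explains the amenorrhea.

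**Step 2. Classification with and without the clause**

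Take a woman with less than 12 months of amenorrhea, none of the listed surgery or conditions, not using hormones, and one FSH in the postmenopausal range. She is under 45 if that limit applies.

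- With the clause: not of childbearing potential.
- Without it: she meets no limb of the definition, so the Note makes her of childbearing potential.

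**Step 3. What depends on the classification**

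| Requirement | Source | Childbearing potential | Classed out by the clause |
|---|---|---|---|
| Contraception on study and for 4 months after last dose | Criterion 217; 6.2.4.10.2 | Required | Not required |
| Pregnancy test at screening | 7.2.1; Table 5, footnote f | Required | Not required |
| Pregnancy test on treatment | 7.2.2: "Serum or urine pregnancy test for female subjects of childbearing potential: Additional, on-treatment pregnancy testing may be performed"; Table 5, footnote f | Required | Not required |
| Pregnancy test at safety follow-up | 7.2.3: "serum or urine pregnancy test for female subjects of childbearing potential" | Required | Not required |

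Stages with a required test: 1 + 1 + 1 = 3 for a woman of childbearing potential, and 0 + 0 + 0 = 0 for a woman released by the clause.

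**Step 4. How the clause would come into use**

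FSH does not appear in Table 5, in Table 6 (whose endocrine panel is TSH, T3 or FT3, FT4 and cortisol) or in the screening list in 7.2.1. The clause acts only when a site obtains or already holds an FSH result.

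**Step 5. Whether another rule catches her**

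- Criterion 219 excludes a positive pregnancy test, but no test is required of her.
- Criterion 220 excludes only women who plan a pregnancy.
- Extra on-treatment testing is at the investigator's discretion.
- Section 6.2.4.10.3 (removal from treatment) and section 9.3 (monitoring and reporting) act once a pregnancy has occurred.

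**The case against.** The best defence is that the FSH clause is itself part of the definition. It opens by addressing women without 12 months of amenorrhea, so such a woman meets the definition by a written alternative route and does not fail it. Nothing in the documents says that one postmenopausal-range FSH is inadequate in a woman not using hormones. That *not sufficient* was intended is only an inference from the wording. The childbearing definitions were also added in Amendment 1, which followed European regulatory review.

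The wording does permit the alternative-route reading. It leaves the result unchanged: one measurement still overrides the 12 months, the confirming role given to FSH just before becomes pointless, and the narrowest reading still gives younger women the looser test. The finding does not depend on what the drafters intended.

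A second defence points to further safeguards: country-specific contraception supplements, counselling on fetal risk, pregnancy monitoring through 7 months after AMG 820 or 4 months after pembrolizumab, and the investigator's discretion under criterion 223. These reduce the exposure. They are local, discretionary or reactive, so they do not replace required contraception and testing.

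The points on scale stand. The count of 3 to 0 is of study stages, not of women or of risk. No age or sex distribution is given for this population with advanced colorectal, pancreatic or lung cancer. Amendment 2 records that the sponsor has decided to stop investigating the combination, which lowers the value of an eligibility correction. It does not remove it: section 3.5.1 allows treatment for up to 24 months, and the classification continues to govern testing and contraception for women already enrolled.

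**Conclusion.** The concern holds. As written, criterion 217 allows a woman who has not had 12 months without menses to be classed as not of childbearing potential on a single FSH measurement. For each such woman, required pregnancy testing falls from three study stages to none, and the contraception requirement ceases to apply.

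The conclusion rests on the current wording of criterion 217 and on the restriction of the contraception and testing rules to women of childbearing potential. It holds under the literal reading and under both narrower ones. How many women are affected is unknown, and the clause matters only where a site uses an FSH result. This is a participant-safety correction that should be made; it has no bearing on any endpoint, analysis or decision rule.

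**What to change.** Make the 12-month definition govern. Either delete the last FSH clause, or reword it to say that without 12 months of amenorrhea a single FSH measurement is **not** sufficient. Women without the 12 months, and without the listed surgery or condition, then default to childbearing potential under the existing Note. The confirming use of FSH in women under 45 can stay as it is.

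In the same edit, correct the cross-reference in 6.2.4.10.2, which points to criterion 214 (HIV) and should point to 217. This is clerical and carries no weight in the finding.

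The cost is one clause in the protocol and a memo to sites. Any woman reclassified would need contraception and the pregnancy tests already in the schedule; no new procedure is added.

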5. SUBJECT ENROLLMENT

Before subjects begin participation in any study-specific activities/procedures, Amgen requires a copy of the site's written IRB/IEC approval of the protocol, informed consent form, and all other subject information and/or recruitment material, if applicable (see [Section 11.2](#)). All subjects must personally sign and date the IRB/IEC and Amgen approved informed consent form before commencement of study-specific activities/procedures.

A subject is considered enrolled when the investigator decides that the subject has met all eligibility criteria. The investigator is to document this decision and date, in the subject's medical record and in/on the enrollment case report form (CRF).

Each subject who enters into the screening period for the study (defined when the subject signs the informed consent) receives a unique subject identification number before any study-related activities/procedures are performed. The subject identification number will be assigned manually. This number will be used to identify the subject throughout the clinical study and must be used on all study documentation related to that subject. Subjects who do not meet all eligibility criteria may be rescreened at the discretion of the investigator. If a subject is being rescreened, he or she may need to reconsent to the study to ensure that the IRB/IEC approved main informed consent form is signed within 28 days of enrollment. Subjects who are determined not eligible after rescreen must be screen-failed and the reason for the screen-failure provided. Subjects may only be enrolled once into this study.

The subject identification number must remain constant throughout the entire clinical study; it must not be changed after initial assignment, including if a subject is rescreened.

5.1 Treatment Assignment

All subjects enrolled into the study will receive open-label AMG 820 in combination with pembrolizumab. The treatment assignment date is to be documented in the subject's medical record.

6. TREATMENT PROCEDURES

6.1 Classification of Product(s) and/or Medical Device(s)

The Amgen Investigational Product used in this study is AMG 820.

The Non-Amgen Investigational product(s) used in this study is pembrolizumab. The Investigational Product Instruction Manual (IPIM), a document external to this protocol, contains detailed information regarding the storage, preparation, destruction, and administration of AMG 820 and pembrolizumab.

6.2 Investigational Product

AMG 820 and pembrolizumab will be administered intravenously Q3W on the same day in sequence. The recommended starting dose of AMG 820, 1400 mg, is guided by the AMG 820 First in Human study. Pembrolizumab will be administered at 200 mg and will remain unchanged during the course of the study. If the treatment combination is not well tolerated during Study Part 1, AMG 820 will be de-escalated to pre-specified nominal dose levels, 1100 mg and 800 mg.

AMG 820 must be administered before pembrolizumab on the same treatment day. The pembrolizumab infusion is to begin 15 minutes following the end of the AMG 820 infusion.

6.2.1 Amgen Investigational Product: AMG 820

AMG 820 will be manufactured and packaged by Amgen Inc. and distributed using Amgen clinical study drug distribution procedures. AMG 820 will be presented as a sterile, clear, colorless to slightly yellow frozen liquid in 20 mL glass vials. Each glass vial will contain 3.0 mL of AMG 820 with a concentration of 70 mg/mL.

6.2.1.1 Dosage, Administration, and Schedule: AMG 820

AMG 820 must be prepared and administered by a qualified healthcare professional. Subjects should be assessed clinically for adverse events/toxicity prior to each dose using the CTCAE version 4 ([Appendix A](#)). Complete blood count with differential and chemistry panels including liver enzyme laboratory tests (ALT and AST) and total bilirubin should be obtained according to the Schedule of Assessments ([Table 5](#)) and the results should be checked within 2 days prior to each treatment.

Each cycle of AMG 820 will be 3 weeks. The initial cohort will treat subjects with 1400 mg AMG 820 plus 200 mg pembrolizumab Q3W. All subsequent doses will be administered Q3W (\pm 3) days. The treatment cycle interval may be increased due to toxicity as described in [Section 6](#). AMG 820 must be administered before pembrolizumab on treatment days. Lower AMG 820 dose levels may be explored based on emerging safety data during study part 1. If a subject requires corticosteroid dosing of > 10 mg prednisone daily (or equivalent) as supportive care, AMG 820 and pembrolizumab dosing must be withheld until the corticosteroid dose has decreased to \leq 10 mg prednisone daily (or equivalent).

AMG 820 will be diluted with the appropriate amount of 0.9% NaCl for a total volume of 100 mL. The final concentration of the AMG 820 will be 14 mg/mL (1400 mg total dose).

AMG 820 preparations will be administered via intravenous (IV) infusion, through a 0.22 μ m, low protein binding filter, over a 60-minute period during the first dosing administration. If the first administration is well-tolerated, the investigator may adopt a 30-minute infusion period for subsequent infusions. A physician or medical staff involved in study evaluation must be available during the administration of the investigational product to assess and treat adverse events that may arise during dosing. Subjects will be monitored in the clinic for at least 2 hours or longer if necessary, following dosing of drug combination for the first 3 cycles and as needed thereafter.

The effects of overdose of this product are not known.

Subjects will be treated with AMG 820 plus pembrolizumab until subjects experience confirmed PD as per irRECIST, intolerance to study treatment, or until the end of study, whichever occurs first. The dose, start date, and lot number of AMG 820 are to be recorded on each subject's CRF.

